### **6.5.2. Participants with Impaired Hepatic Function (Cohorts 2, 3, and 4)**

Participants are permitted to be on stable doses of background medications for the management of their concomitant medical condition(s). Whenever possible, attempts must be made to not alter the doses and regimens of the concomitant medications after Day 1 and until the follow-up contact.

Participants on certain medications, at the screening visit, are excluded from the study (see [Appendix 9](#) for details regarding prohibited prior/concomitant medications).

### **6.5.3. Rescue Medicine**

There is no rescue therapy to reverse the AEs observed with PF-06882961; standard medical supportive care must be provided to manage the AEs.

### **6.6. Dose Modification**

Dose modification of PF-06882961 is not allowed.

### **6.7. Intervention After the End of the Study**

No intervention will be provided to study participants at the end of the study.

## **7. DISCONTINUATION OF STUDY INTERVENTION AND PARTICIPANT DISCONTINUATION/WITHDRAWAL**

### **7.1. Discontinuation of Study Intervention**

Since this is a single-dose study, this section is not applicable.

### **7.2. Participant Discontinuation/Withdrawal From the Study**

A participant may withdraw from the study at any time at his/her own request. Reasons for discontinuation from the study include the following:

- Refused further follow-up;
- Lost to follow-up;
- Death;
- Study terminated by sponsor.

At the time of discontinuing from the study, if possible, an early discontinuation visit should be conducted. See the [SoA](#) for assessments to be collected at the time of study discontinuation and follow-up and for any further evaluations that need to be completed.

If a participant withdraws from the study, he/she may request destruction of any remaining samples taken and not tested, and the investigator must document any such requests in the site study records and notify the sponsor accordingly.

If the participant withdraws from the study and also withdraws consent (see [Section 7.2.1](#)) for disclosure of future information, no further evaluations should be performed and no additional data should be collected. The sponsor may retain and continue to use any data collected before such withdrawal of consent.

Lack of completion of all or any of the withdrawal/early termination procedures will not be viewed as protocol deviations so long as the participant's safety was preserved.

### **7.2.1. Withdrawal of Consent**

Participants who request to discontinue receipt of study intervention will remain in the study and must continue to be followed for protocol-specified follow-up procedures. The only exception to this is when a participant specifically withdraws consent for any further contact with him or her or persons previously authorized by the participant to provide this information. Participants should notify the investigator in writing of the decision to withdraw consent from future follow-up, whenever possible. The withdrawal of consent should be explained in detail in the medical records by the investigator, as to whether the withdrawal is only from further receipt of study intervention or also from study procedures and/or posttreatment study follow-up, and entered on the appropriate CRF page. In the event that vital status (whether the participant is alive or dead) is being measured, publicly available information should be used to determine vital status only as appropriately directed in accordance with local law.

### **7.3. Lost to Follow up**

A participant will be considered lost to follow-up if he or she repeatedly fails to return for scheduled visits and is unable to be contacted by the study site.

The following actions must be taken if a participant fails to return to the clinic for a required study visit:

- The site must attempt to contact the participant and reschedule the missed visit as soon as possible and counsel the participant on the importance of maintaining the assigned visit schedule and ascertain whether or not the participant wishes to and/or should continue in the study;
- Before a participant is deemed lost to follow-up, the investigator or designee must make every effort to regain contact with the participant (where possible, 3 telephone calls and, if necessary, a certified letter to the participant's last known mailing address or local equivalent methods). These contact attempts should be documented in the participant's medical record;

- Should the participant continue to be unreachable, he/she will be considered to have withdrawn from the study.

## 8. STUDY ASSESSMENTS AND PROCEDURES

The investigator (or an appropriate delegate at the investigator site) must obtain a signed and dated ICD before performing any study-specific procedures.

Study procedures and their timing are summarized in the [SoA](#). Protocol waivers or exemptions are not allowed.

Safety issues should be discussed with the sponsor immediately upon occurrence or awareness to determine whether the participant should continue or discontinue study intervention.

Adherence to the study design requirements, including those specified in the [SoA](#), is essential and required for study conduct.

All screening evaluations must be completed and reviewed to confirm that potential participants meet all eligibility criteria. The investigator will maintain a screening log to record details of all participants screened and to confirm eligibility or record reasons for screening failure, as applicable.

Participants will be screened within 28 days prior to administration of the study intervention to confirm that they meet the study population criteria for the study. If the time between screening and dosing exceeds 28 days as a result of unexpected delays (eg, delayed drug shipment), then participants do not require rescreening if the laboratory results obtained prior to first dose administration meet eligibility criteria.

Every effort should be made to ensure that protocol-required tests and procedures are completed as described. However, it is anticipated that from time to time there may be circumstances outside the control of the investigator that may make it unfeasible to perform the test. In these cases, the investigator must take all steps necessary to ensure the safety and well-being of the participant. When a protocol-required test cannot be performed, the investigator will document the reason for the missed test and any corrective and preventive actions that he or she has taken to ensure that required processes are adhered to as soon as possible. The study team must be informed of these incidents in a timely manner.

ECGs and vital sign assessments (pulse rate and BP) should be collected prior to any blood draw. If an IV catheter is utilized for blood sample collections, ECGs and vital sign assessments (pulse rate and BP) should be collected prior to the insertion of the catheter.

For samples being collected and shipped, detailed collection, processing, storage, and shipment instructions and contact information will be provided to the investigator site prior to initiation of the study.

The total blood sampling volume for individual participants in this study is approximately 175 mL. The actual collection times of blood sampling may change. Additional blood samples may be taken for safety assessments at times specified by Pfizer, provided the total volume taken during the study does not exceed 550 mL during any period of 60 consecutive days.

To prepare for study participation, participants will be instructed on the information in the [Lifestyle Considerations](#) and [Concomitant Therapy](#) sections of the protocol.

## **8.1. Efficacy Assessments**

Not Applicable.

## **8.2. Safety Assessments**

Planned time points for all safety assessments are provided in the [SoA](#). Unscheduled clinical laboratory measurements may be obtained at any time during the study to assess any perceived safety issues.

### **8.2.1. Physical Examinations**

A complete physical examination will include, at a minimum, head, ears, eyes, nose, mouth, skin, heart and lung examinations, lymph nodes, and gastrointestinal, musculoskeletal, and neurological systems.

A limited physical examination will include, at a minimum, assessments of general appearance, the respiratory and cardiovascular systems, and participant-reported symptoms.

Physical examinations may be conducted by a physician, trained physician's assistant, or nurse practitioner as acceptable according to local regulation.

Height and weight will also be measured and recorded as per the [SoA](#). For measuring weight, a scale with appropriate range and resolution is used and must be placed on a stable, flat surface. Participants must remove shoes, bulky layers of clothing, and jackets so that only light clothing remains. They must also remove the contents of their pockets and remain still during measurement of weight.

### **8.2.2. Vital Signs**

Blood pressure and pulse rate will be measured as defined in the [Schedule of Activities](#). Additional collection times, or changes to collection times of blood pressure and pulse rate will be permitted, as necessary, to ensure appropriate collection of safety data.

- **Single, seated** BP/pulse rate will be measured with the participant's arm supported at the level of the heart, and recorded to the nearest mmHg, following a rest of **≥5 minutes**;

- Same arm (preferably the dominant arm) will be used for BP/pulse rate assessment throughout the study;
- BP/pulse rate assessment should not be taken from the arm with an IV catheter, if placed;
- Participants should be instructed not to speak during BP/pulse rate measurements.

The same properly sized and calibrated BP cuff will be used to measure BP each time. The use of an automated device for measuring BP and pulse rate is acceptable; however, when done manually, pulse rate will be measured in the brachial/radial artery for at least 30 seconds. When the timing of these measurements coincides with a blood collection, BP and pulse rate should be obtained prior to the nominal time of the blood collection.

Additional collection times, or changes to collection times, of BP and pulse rate will be permitted, as necessary, to ensure appropriate collection of safety data.

#### 8.2.2.1. Temperature

Body temperature will be measured at the timepoints listed in the [SoA](#). No eating, drinking, or smoking is allowed for 15 minutes prior to this measurement.

#### 8.2.3. Electrocardiograms

**Supine** standard 12-lead ECGs utilizing limb leads (with a 10 second rhythm strip) should be collected at times specified in the [SoA](#) section of this protocol using an ECG machine that automatically calculates the heart rate and measures PR, QT, and QTc and QTcF intervals and QRS complex. Alternative lead placement methodology using torso leads (eg, Mason-Likar) is not recommended given the potential risk of discrepancies with ECGs acquired using standard limb lead placement. All scheduled ECGs should be performed after the participant has rested quietly for at least **10 minutes** in a supine position.

To ensure safety of the participants, a qualified individual at the investigator site will make comparisons to baseline measurements. Additional ECG monitoring will occur if a) a postdose QTcF interval is increased by  $\geq 60$  msec from the baseline **and** is  $> 450$  msec; or b) an absolute QTcF value is  $\geq 500$  msec for any scheduled ECG. If either of these conditions occurs, then 2 additional ECGs will be collected approximately 2 to 4 minutes apart to confirm the original measurement. If the QTcF values from these repeated ECGs remain above the threshold value, then a single ECG must be repeated at least hourly until QTcF values from 2 successive ECGs fall below the threshold value that triggered the repeat measurement.

If a) a postdose QTcF interval remains  $\geq 60$  msec from the baseline **and** is  $> 450$  msec; or b) an absolute QTcF value is  $\geq 500$  msec for any scheduled ECG for greater than 4 hours (or sooner, at the discretion of the investigator); or c) QTcF intervals get progressively longer, the participant should undergo continuous ECG monitoring. A cardiologist should be consulted if QTc intervals do not return to less than the criterion listed above after 8 hours of monitoring (or sooner, at the discretion of the investigator).

In some cases, it may be appropriate to repeat abnormal ECGs to rule out improper lead placement as contributing to the ECG abnormality. It is important that leads be placed in the same positions each time in order to achieve precise ECG recordings. If a machine-read QTcF value is prolonged, as defined above, repeat measurements may not be necessary if a qualified medical provider's interpretation determines that the QTcF values are in the acceptable range.

ECG values of potential clinical concern are listed in [Appendix 7](#).

#### **8.2.4. Clinical Safety Laboratory Assessments**

See [Appendix 2](#) for the list of clinical safety laboratory tests to be performed and the **SoA** for the timing and frequency. All protocol-required laboratory assessments, as defined in [Appendix 2](#), must be conducted in accordance with the laboratory manual and the **SoA**. Unscheduled clinical laboratory measurements may be obtained at any time during the study to assess any perceived safety issues.

The investigator must review the laboratory report, document this review, and record any clinically relevant changes occurring during the study in the AE section of the CRF. Clinically significant abnormal laboratory findings are those which are not associated with the underlying disease, unless judged by the investigator to be more severe than expected for the participant's condition.

All laboratory tests with values considered clinically significantly abnormal during participation in the study or within 5 days after the last dose of study intervention should be repeated until the values return to normal or baseline or are no longer considered clinically significant by the investigator or medical monitor.

If such values do not return to normal/baseline within a period of time judged reasonable by the investigator, the etiology should be identified and the sponsor notified.

See [Appendix 6](#) for suggested actions and follow-up assessments in the event of potential drug-induced liver injury.

### **8.2.5. COVID-19 Specific Assessments**

During the screening period, participants will be assessed for COVID-19 related symptoms and risks per local regulations and institutional policies. Participants will also be tested for SARS CoV-2 infection at the timepoints specified in the [SoA](#). Additional testing may be required by local regulations, institutional policies or by the Principal Investigator. The test result must be negative in order for a participant to proceed with admission on Day -1 and dosing on Day 1. COVID-19 tests may be conducted at central or local labs.

### **8.2.6. Glucose Monitoring**

While hypoglycemia is not expected in the study participants, FPG will be measured with laboratory assessments as noted in the [SoA](#). In addition, as a precaution, participants should be monitored for the signs and symptoms associated with hypoglycemia.

Any episode of hypoglycemia must be captured on the AE CRF with specific details captured on the HAE Form CRF. For the definition of a hypoglycemic episode and severity categorization see [Section 8.2.6.1](#) below.

#### **8.2.6.1. Definition and Severity of Hypoglycemic Adverse Event (HAE)**

The investigator must assess the glucose values reported by the central laboratory, as well as any signs or symptoms reported by the study participant.

HAE is defined as one of the following:

- a. Asymptomatic hypoglycemia: An event not accompanied by typical symptoms of HAE but a glucose value of <70 mg/dL (3.9 mmol/L) using either glucometer (fingerstick blood glucose) at the study site or sponsor-identified central laboratory (plasma glucose).
- b. Documented symptomatic hypoglycemia: An event during which typical symptoms of HAE are accompanied with a glucose value of <70 mg/dL (3.9 mmol/L), using glucometer at the study site or sponsor identified central laboratory, and the clinical picture includes prompt resolution with food intake, subcutaneous glucagon, or IV glucose.
- c. Probable symptomatic hypoglycemia: An event during which symptoms of HAE are not accompanied by a glucose determination but was presumably caused by a glucose concentration of <70 mg/dL (3.9 mmol/L), and the clinical picture includes prompt resolution with food intake, subcutaneous glucagon, or IV glucose.

Each episode of HAE must be categorized with respect to severity. In order to characterize the event as severe, all 3 criteria below must be met:

1. The participant was unable to treat him/herself. Neurologic impairment, and not the age of the participant, is the explanation for why the participant could not treat him/herself and required the assistance of another person.

2. The participant exhibited at least 1 of the following neurological symptoms:
  - Memory loss;
  - Confusion;
  - Uncontrolled behavior;
  - Irrational behavior;
  - Unusual difficulty in awakening;
  - Suspected seizure;
  - Seizure;
  - Loss of consciousness.
3. Either:
  - If blood glucose was measured and was  $\leq 54$  mg/dL (2.7 mmol/L) using glucometer (or central laboratory); or
  - If blood glucose was not measured, the clinical manifestations were reversed by oral carbohydrates, subcutaneous glucagon, or IV glucose.

Events that do not meet all the criteria above for severe HAE are characterized as mild or moderate in severity.

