### Assessment of Intensity

The investigator will make an assessment of intensity for each AE and SAE reported during the study and assign it to 1 of the following categories:

- Mild: An event that is easily tolerated by the participant, causing minimal discomfort and not interfering with everyday activities.
- Moderate: An event that causes sufficient discomfort and interferes with normal everyday activities.
- Severe: An event that prevents normal everyday activities. An AE that is assessed as severe should not be confused with an SAE. Severe is a category utilized for rating the intensity of an event; and both AEs and SAEs can be assessed as severe.

An event is defined as “serious” when it meets at least 1 of the predefined outcomes as described in the definition of an SAE, NOT when it is rated as severe.

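### The glucose limit for a severe hypoglycemic event is printed as 54 mg/dL and 2.7 mmol/L, which are two different concentrations

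*Protocol*

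**What the plan says.** Protocol Section 8.2.6 requires every episode to be recorded: "Any episode of hypoglycemia must be captured on the AE CRF with specific details captured on the HAE Form CRF". Section 8.2.6.1 then defines an HAE and its severity.

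- **Definition of an HAE.** The asymptomatic category uses "a glucose value of <70 mg/dL (3.9 mmol/L) using either glucometer (fingerstick blood glucose) at the study site". The documented and probable symptomatic categories repeat the same pair of values.
- **Severe grade.** All three criteria must hold: the participant could not self-treat because of neurologic impairment; at least one listed neurological symptom was present; and, if glucose was measured, it was "\leq 54$ mg/dL (2.7 mmol/L) using glucometer (or central laboratory". If glucose was not measured, reversal by carbohydrate, glucagon or IV glucose takes the place of the reading.
- **Otherwise.** "Events that do not meet all the criteria above for severe HAE are characterized as mild or moderate in severity".

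The glucose may come from a site glucometer or the central laboratory. The protocol does not say in which unit either reports, or which unit governs. The SAP does not restate the limit.

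**The concern.** A threshold printed in two units should be one concentration. Here the pair used to define an HAE is consistent, and the pair used to grade one is not. When glucose was measured and criteria 1 and 2 are met, this number alone separates severe from mild or moderate, so two sites could grade the same reading differently, depending on which figure they apply.

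What is at stake is the consistency of a required safety classification. Treatment-emergent adverse events are the secondary endpoint, and hypoglycemia is among the potential risks in Protocol Section 2.3.1. There is a further consideration, which is an inference and not a protocol statement. Cohorts 2 to 4 may include participants with Grade 1 or 2 encephalopathy (Appendix 8), whose signs overlap with some symptoms in criterion 2. For them the measured glucose is the most objective part of the definition.

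**Working it through.** **Inputs, all from Protocol Section 8.2.6.1**

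- HAE definition: 70 mg/dL = 3.9 mmol/L.
- Severe limit: 54 mg/dL = 2.7 mmol/L.
- Assumption from outside the documents, used only as a second check: glucose molar mass about 180.16 g/mol, which gives 18.016 mg/dL per mmol/L.

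**Step 1. Try to reproduce the printed figures.** Formula: mmol/L = (mg/dL) / factor.

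- With 18.016, 70 / 18.016 = 3.89, which rounds to the printed 3.9.
- With 18.016, 54 / 18.016 = 3.00. The printed 2.7 is not reproduced.

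**Step 2. Use only the section's own scale.**

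- Factor: 70 / 3.9 = 17.95 mg/dL per mmol/L.
- 54 / 17.95 = 3.01 mmol/L.
- 2.7 × 17.95 = 48.5 mg/dL (48.6 with 18.016).
- Relative error: (3.0 − 2.7) / 3.0 = 10%.

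**Step 3. Can rounding explain it?**

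- 3.9 covers 3.85 to 3.95, so the factor lies between 70 / 3.95 = 17.72 and 70 / 3.85 = 18.18.
- 54 mg/dL then lies between 54 / 18.18 = 2.97 and 54 / 17.72 = 3.05 mmol/L.
- 2.7 covers 2.65 to 2.75, so it corresponds to between 2.65 × 17.72 = 47.0 and 2.75 × 18.18 = 50.0 mg/dL.
- The interval 47.0 to 50.0 does not reach 54. Rounding is excluded.

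**Step 4. Which readings are affected?** Whole-number readings, factor 18.016, criteria 1 and 2 assumed met:

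| mg/dL | mmol/L | to one decimal | at or below 54 mg/dL | at or below 2.7 mmol/L (one decimal) |
|---|---|---|---|---|
| 48 | 2.66 | 2.7 | yes | yes |
| 49 | 2.72 | 2.7 | yes | yes |
| 50 | 2.78 | 2.8 | yes | no |
| 51 | 2.83 | 2.8 | yes | no |
| 52 | 2.89 | 2.9 | yes | no |
| 53 | 2.94 | 2.9 | yes | no |
| 54 | 3.00 | 3.0 | yes | no |
| 55 | 3.05 | 3.1 | no | no |

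On a continuous scale the discordant band runs from about 48.6 to 54 mg/dL, a width of 54 − 48.6 = 5.4 mg/dL. With mmol/L reported to one decimal it is the five readings 50 to 54. If mmol/L is not rounded, 49 mg/dL (2.72) is discordant too.

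**The case against.** The arithmetic is not in dispute; the weight is. The strongest case for treating this as purely editorial has four parts.

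1. **The leading unit looks clear.** Section 8.2.6.1 prints mg/dL first throughout, with mmol/L in brackets, and the fasting-glucose exclusion in Section 5.2.1 is in mg/dL only. The bracket may simply be a faulty convenience conversion. This makes divergent grading less likely, but it does not show which value was intended, and no sentence says that mg/dL governs.
2. **Little follows from the grade.** The general intensity scale in Section 10.3.3 defines severe by its effect on everyday activities and uses no glucose value, so an event meeting criteria 1 and 2 would probably be severe on that scale anyway. The same section separates severity from seriousness: "An AE that is assessed as severe should not be confused with an SAE". No treatment, stopping or expedited-reporting rule uses the HAE category, and the SAP plans no summary by it. This stands, and it limits the consequence to the HAE severity category itself.
3. **The trigger is improbable.** Section 8.2.6 opens with "While hypoglycemia is not expected in the study participants". Participants with documented type 2 diabetes are excluded, one 20 mg dose is given, and the program to date has reported one HAE, which was mild (Sections 2.2.2.1 and 2.3.1). This also stands.
4. **The edge of the band depends on rounding.** Whether 49 mg/dL is discordant turns on the reporting precision in mmol/L, which the documents do not give. That is true and changes the count by one reading.

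These points reduce how much the error matters. None of them makes the two figures agree.

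**Conclusion.** The concern holds. The severe-HAE limit is printed as two concentrations that differ by 0.3 mmol/L, or about 5.4 mg/dL, with the mmol/L figure 10% below the conversion of 54 mg/dL. The section's own 70 mg/dL = 3.9 mmol/L pair is enough to show this, and the molar-mass factor agrees.

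The effect is narrow. It needs a measured glucose, criteria 1 and 2 already met, and a reading of 50 to 54 mg/dL (assuming mmol/L to one decimal). Unit-dependent grading is possible but not shown, because the reporting units are not stated. No pharmacokinetic endpoint, sample-size figure or SAP model is affected. The figure should still be corrected, because it is an operative rule in the current protocol and a required classification cannot carry two cut-offs.

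**What to change.** The sponsor should state which of the two values was intended and reconcile them, so that criterion 3 in Section 8.2.6.1 carries one threshold with a correct conversion. The HAE form in the CRF, and any site instructions that repeat the limit, should be checked against it. Naming the governing unit in the same sentence would remove the remaining ambiguity. Which value is clinically right is for the sponsor to say and is not proposed here.

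The cost is one corrected figure in the protocol and a check of the CRF form. Doing it before any event occurs avoids having to regrade one afterwards.
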